6.2. Randomized Treatment

Subjects will be randomized to receive one of two treatments described below.

Treatment A: BPL HRIG + rabies vaccine (RabAvert®).

A 20 IU/kg dose of BPL HRIG will be given on Day 0 via IM injection. The volume to be injected will be based upon the subject's weight on Day 0 and BPL HRIG actual potency (see pharmacy manual). A maximum of 5 mL will be administered to each lateral thigh and a maximum 2.0 mL to the deltoid muscle. The gluteal muscle will not be used for IM injection due to the increased variability of absorption from this injection site and the risk of injury to the sciatic nerve.

The total volume will be split between the injection sites as follows:

Table 5: Treatment A -total volume to be split between the injection sites

Injection number	Volume to be injected	Site of injection
1	up to 5 mL depending on bodyweight	left lateral thigh muscle
2	up to 5 mL depending on bodyweight	right lateral thigh muscle
3 (if required)	up to 2 mL depending on bodyweight	left deltoid muscle

A 1.0 ml dose of active vaccine (2.5 IU/ml) will be given IM on 5 occasions: on Days 0, 3, 7, 14, and 28. On day 0, the vaccine will be administered to the right deltoid muscle. The subsequent doses of vaccine on days 3, 7, 14, and 28 may be administered to the right or the left deltoid muscle.

The vaccine dose should never be administered into the same anatomical site as the HRIG.

Treatment B: FDA-approved comparator HRIG (HyperRAB[®] S/D) + rabies vaccine (RabAvert[®])

A 20 IU/kg dose of comparator HRIG will be given on Day 0 via IM injection. The volume to be injected will be based upon the subject's weight on Day 0 and BPL HRIG actual potency (see pharmacy manual). A maximum of 5 mL will be administered to each lateral thigh and a maximum 2.0 mL to the deltoid muscle. The gluteal muscle will not be used for IM injection due to the increased variability of absorption from this injection site and the risk of injury to the sciatic nerve.

The total volume will be split between the injection sites as follows:

Table 6: Treatment B -total volume to be split between the injection sites

Injection number	Volume to be injected	Site of injection
1	Up to 5 mL depending on body weight	left lateral thigh muscle
2	up to 5 mL depending on bodyweight	right lateral thigh muscle
3 (if required)	up to 2 mL depending on bodyweight	left deltoid muscle

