7.7. Visit 9: End-of-Study Assessment

An End-of-Study assessment will be conducted at Day 140 (\pm 7 days). The following assessments will be performed:

- Check of any new or changed adverse events and concomitant medications since the last visit
- Physical examination including 12-lead ECG and body weight
- Vital signs: sitting blood pressure (mmHg) after a 5 min rest, pulse rate and respiration rate (see [Section 8.2.8](#))
- Blood samples will be taken for the following assessments:
 - o hematology and serum biochemistry (see [Sections 8.2.4 and 8.2.5](#))
 - o Serum Pregnancy
 - o virology: anti-HIV1&2, HBsAg, anti-HCV (see [Section 8.2.3](#))
 - o rabies virus neutralizing antibodies (see [Section 8.1.4](#))
- Reserve blood samples will be taken (see [Section 7.9.1](#))
- A urine sample will be collected for urinalysis
- An archive serum sample will be taken (see [Section 7.9.2](#)) for long-term storage at -70°C or lower for 15 years.

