2.2 Adverse Events Temporally Associated with the Injection

Unless clearly attributable to other causes any AEs that occur from the injection until Day 3 after the injection will be recorded as temporally related to the injection.

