3.1 Causality

All AEs will be recorded in the CRF/eCRF, whether considered to be related or unrelated to the treatment. The record will include the following: brief description of event (preferably a diagnosis), date and time started and stopped severity, outcome, actions taken and classification of the AE. The Investigator should also evaluate the probability of a causal relationship of the AE to each medication administered during the study according to the following criteria as:

-
1. Unrelated Clinical event with an incompatible time relationship to study medication administration, or that could be explained by underlying disease or other drugs or chemicals, or is incontrovertibly not related to the IMP.
 2. Unlikely Clinical event whose time relationship to study medication administration makes a causal connection improbable, but that could plausibly be explained by underlying disease or other drugs or chemicals.
 3. Possible Clinical event with a reasonable time relationship to study medication administration, but that could also be explained by concurrent disease or other drugs or chemicals.
 4. Probable Clinical event with a reasonable time relationship to study medication administration, and is unlikely to be attributed to concurrent disease or other drugs or chemicals.
 5. Very likely / certain Clinical event with plausible time relationship to study medication administration, and that cannot be explained by concurrent disease or other drugs or chemicals.

Study medication is defined as those investigational compounds or their controls and vaccines used in the study.

It will be assumed that for all adverse events classified as “probably related”, “possibly related” or “very likely / certainly related” to the study medication, there is reasonable likelihood that the adverse event was causally related to the product. All such adverse events will be regarded as “causally related” to the study medication.

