5. The geometric mean titers (GMTs) for anti-rabies antibody titer at Visit 6-9 will be compared between treatment groups. Descriptive statistics and visual inspections will be reported as appropriate. No formal hypotheses testing will be performed.

g. EXPLORATORY PK ANALYSES

The following PK parameters for anti-rabies antibody concentrations will be summarized for both treatment groups:

- C_{\max} [IU/mL]
- T_{\max} [day]
- area under the concentration vs time curve to the last measurable concentration (AUC_{0-t}) [day*IU/mL]
- apparent terminal rate constant (λ_z) [day⁻¹]
- AUC_{0-7d} [day*IU/mL]
- area under the concentration vs time curve to infinity ($AUC_{0-\infty}$), if appropriate

- $C_{\max}/AUC_{0-\infty}$ [or C_{\max}/AUC_{0-t} if $AUC_{0-\infty}$ cannot be estimated]
- half-life ($t_{1/2}$), if appropriate

Non-compartmental PK methods will be utilized to calculate the subject level PK parameters. C_{\max} , AUC_{0-t} , AUC_{0-7d} , $AUC_{0-\infty}$, apparent terminal rate constant (λ_z), and $t_{1/2}$ will be dose normalized by dividing the raw PK parameters by the actual dose the subject received. A t-test will compare the PK and dose-normalized PK parameters between treatment groups. Log-transformations will be performed as necessary during statistical analysis when appropriate.

h. ADVERSE EVENT REPORTING

Adverse events (AEs) will be reported by the MedDRA system organ class and preferred term. Only treatment emergent AEs (i.e. beginning after dosing with BPL HRIG / vaccine or comparator HRIG / vaccine) will be included in the summary tables. All AEs will be included in the data listings.

Treatment-related AEs will be defined as events recorded as having a possible, probable or very likely/certain causality to treatment. AEs leading to withdrawal will be defined as events where the subject's participation in the study was discontinued as a result of the AE.

AEs will be summarized descriptively for all subjects and by treatment group. The denominator used for the calculation of percentages will be the number of subjects in the safety population per treatment group. For all AE summaries described below, counting will be performed by subject and event. For counts by subject, subjects experiencing the same event more than once will have that event counted only once within each system organ class and once within each preferred term.

The following summaries of treatment-emergent AEs will be provided:

SUMMARY OF AEs

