- The number and percentage of subjects reporting AEs, serious AEs, study medication-related AEs, AEs leading to withdrawal and AEs leading to death.
- The number of AEs, serious AEs, study medication-related AEs, AEs leading to withdrawal and AEs leading to death.

SUMMARY OF AEs BY SEVERITY OF EVENT

The number and percentage of subjects reporting AEs, and study medication-related AEs, will be summarized by the system organ class and by the preferred term. The severity of event will be recorded once per subject for each term as the maximum severity experienced by each subject (i.e. where the order of most severe to least severe is given by: severe, moderate and then mild).

SUMMARY OF AEs BY CAUSALITY

The number and percentage of subjects reporting AEs will be summarized by the system organ class and by the preferred term. The causality will be recorded once per subject for each term giving the most likely relationship to study medication (i.e. in the order: very likely/certain, probable, possible, unlikely and then unrelated).

i. SENSITIVITY ANALYSES

Sensitivity analyses will be performed to assess the impact on the primary PK analysis of non-compliers within the ITT population, missing primary endpoints, and timing of vaccine dosing.

POTENTIAL INTERACTION

Before treatment unblinding, timing of vaccine dosing and PK sampling, if not performed on the designated day, will be assessed as potential effect modifiers on the association between RVNA levels and treatment group in the primary and secondary PK analysis. A chi-square or fisher's exact test, as appropriate, will be used to measure the association between the dichotomous indicator of receiving dose/PK sampling on the intended day

[yes/no] and target level of RVNA titer reached [yes/no]. If the association is significant at the 0.05 level, a subgroup analysis including only subjects who were dosed/sampled on the target day will be reported in addition to the full analysis.

NON-COMPLIERS AND MISSING DATA

Non-compliers will be defined as subjects who meet one of the following:

- subjects who did not receive the full dose of BPL HRIG/comparator HRIG [not eligible for primary PK population];
- all 3 doses of active rabies vaccine at the time specified [not eligible for primary PK population];
- randomized without meeting all eligibility criteria [REDACTED];
- subjects with any major protocol deviations reported [REDACTED].

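### Systemic AE incidence tables pool Day 0 to Day 140, so an early difference after the single HRIG dose can be partly masked; tables by onset period would show it

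*SAP*

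**What the plan says.** SAP 8.h and Protocol 10.6.1 plan three kinds of AE summary: overall, by severity and by causality. All are restricted to treatment-emergent events, which the SAP defines as "beginning after dosing with BPL HRIG / vaccine or comparator HRIG / vaccine". No end date or sub-period is given, so they run to the end of follow-up: "An End-of-Study assessment will be conducted at Day 140" (Protocol 7.7).

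Counting is by subject and by event. Subject incidence follows a count-once rule: "subjects experiencing the same event more than once will have that event counted only once within each system organ class". Preferred terms are treated likewise. The overall summary gives "The number and percentage of subjects reporting AEs, serious AEs, study medication-related AEs, AEs leading to withdrawal and AEs leading to death", and then the number of events in the same categories. The severity and causality summaries are described as numbers and percentages of subjects, with one record per subject per term.

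Relatedness in these tables is to study medication, which Protocol 6 defines as both HRIGs and the vaccine together. Injection-site reactions are handled separately, by product and by number of injections (Protocol 10.6.2; SAP section 8, Injection Site Observations).

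Protocol Appendix A 2.2 sets a time window: unless another cause is clear, "any AEs that occur from the injection until Day 3 after the injection will be recorded as temporally related to the injection". It does not say which injection is meant. Neither SAP 8.h nor Protocol 10.6.1 refers to this record.

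**The concern.** Objective 4 is the comparative safety and tolerability of BPL HRIG. The only randomized difference is the HRIG product: "A 20 IU/kg dose of BPL HRIG will be given on Day 0 via IM injection", and the comparator likewise once on that day. The vaccine is common to both arms and "will be given IM on 5 occasions: on Days 0, 3, 7, 14, and 28" (Protocol 6.2).

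The two products share systemic terms. Protocol Table 3 lists headache, fever, malaise and fatigue among the HRIG class effects. Protocol 2.8 lists the same four among the most common vaccine reactions. A headache on Day 1 and a headache on Day 29, after vaccine dose 5, are therefore the same entry in a subject-incidence table, and a subject with both counts once.

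Protocol 10.6 says safety will be judged by looking through the summaries for clinically relevant imbalance. If the incidence summaries understate an early systemic imbalance, that reading is weaker than the collected data allow. This matters because Protocol 2.5 states that BPL HRIG has not been studied in a clinical trial, and the study is meant to support a US licence.

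**Working it through.** The plan states no AE rate or safety power, so there is no planned figure to reproduce. The check is the schedule, then the effect of pooling.

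**Schedule** (Protocol 6.2, 7.7; Appendix A 2.2)
- HRIG doses: 1, on Day 0.
- Vaccine doses: 5, of which 5 - 1 = 4 come after Day 0 (Days 3, 7, 14 and 28), the same in both arms.
- If the Appendix A 2.2 window is counted from Day 0, it covers 3 of 140 days. The remainder is 140 - 3 = 137 days.

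**Effect on subject incidence.** Let p1 and p0 be the incidence of a term in the early period in the two arms. Let b be its incidence later, equal in both arms and independent of the early events. With each subject counted once:

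- pooled incidence = 1 - (1 - p)(1 - b)
- pooled difference = (p1 - p0)(1 - b)

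The factor (1 - b) does not depend on p1 or p0. The documents give no incidence by period, so the rates below are assumed: p1 = 25%, p0 = 10%.

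| b | Arm with 25% early | Arm with 10% early | Difference |
|---|---|---|---|
| 0 | 25.0% | 10.0% | 15.0 points |
| 10% | 1 - 0.75 × 0.90 = 32.5% | 1 - 0.90 × 0.90 = 19.0% | 13.5 points |
| 40% | 1 - 0.75 × 0.60 = 55.0% | 1 - 0.90 × 0.60 = 46.0% | 9.0 points |
| 60% | 1 - 0.75 × 0.40 = 70.0% | 1 - 0.90 × 0.40 = 64.0% | 6.0 points |

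**Effect on event counts.** Take 81 subjects per arm, and at most one early and one later event per subject. Expected early events are 81 × 0.25 = 20.25 v 81 × 0.10 = 8.1, an excess of 12.15. Later events add 81b to each arm. At b = 60% that is 48.6 each, giving 68.85 v 56.7. The excess is still 12.15, but it sits on a larger, noisier total.

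**Do other planned outputs recover the early comparison?**
- The related-AE rows and causality table remove events judged unrelated, but keep later vaccine reactions, because study medication includes the vaccine.
- Appendix A 3.1 has causality assessed for each medication, but no planned AE table splits by product.
- All AEs are listed, but a listing is not a summary by arm.
- HRIG-site reactions are separated by product, so local tolerability is not affected.

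**The case against.** The strongest reply is that this asks for one more display in a descriptive safety analysis, and that several stronger readings go too far. Much of that is right.

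- **An early excess would be invisible in every AE table.** A reader might infer this from the count-once rule. That rule governs counts by subject only. The SAP also counts events, and the excess in expected events does not shrink.
- **All reactions to HRIG are diluted.** Not so. Injection-site reactions have their own tables by product.
- **Everything after Day 3 is equal background.** The documents say otherwise. Protocol 2.4 gives a delay of 2-3 days before HRIG is bioavailable and a half-life of about 3-4 weeks, and Protocol 2.9 chose 140 days on that basis. The arms can still differ after Day 3, so the whole-study tables have a purpose and an early table alone would be too narrow.
- **The plan breaks a promise made in Appendix A 2.2.** That section requires events to be recorded as temporally related and promises no table. It names no product, so it may apply to each vaccine injection, and it exempts events clearly due to other causes.
- **The masking is large.** No figure in the documents supports this. Table 3 classes every HRIG effect as rare, and Protocol 2.2 says systemic symptoms after vaccine are rarely reported. Protocol 2.8 does put flu-like symptoms among the most common vaccine reactions, but without rates. If b is near 10%, little is lost.

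What remains is that, for systemic terms, no planned incidence table separates the days after the HRIG dose from those after four further vaccine doses, and no other planned summary makes that split.

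**Conclusion.** The point holds for systemic AEs and for subject incidence. Under independence and equal later incidence b, pooling multiplies an early between-arm difference by (1-b). With the assumed 25% v 10%, the 15 points becomes anything from 13.5 (b = 10%) to 6 (b = 60%). These rates are illustrative and well above the frequency class in Table 3. The factor is the result; the size in this trial cannot be known from the documents. If HRIG effects also appear later, b is not equal in the two arms and the formula no longer applies exactly.

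An early-period table would not isolate HRIG from the Day 0 vaccine dose. Because that dose is the same in both arms, the randomized difference in the period can still be read as a difference between the HRIG products.

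This is a cheap improvement to the safety output, not an error that invalidates it. It does not touch the primary analysis, sample size or alpha.

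**What to change.** In SAP 8.h and Protocol 10.6.1:

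1. State which injection Appendix A 2.2 refers to.
2. Add descriptive overall, SOC/PT and maximum-severity tables of treatment-emergent AEs by arm and onset period: (1) from the Day 0 HRIG injection until just before vaccine dose 2 at Visit 3; (2) from vaccine dose 2 to Day 140.
3. Apply the count-once rule within each period, and show the period 1 risk difference between arms without a hypothesis test, in keeping with Protocol 10.6.
4. Base the cut on date and time of AE onset and of injection, with a stated rule for Day 3 onsets that have no time. Appendix A 3.1 asks for "date and time started and stopped" and Protocol 6.3 records injection times, but Appendix A 2.3 lists only the date of first occurrence.
5. Describe period 1 as based on the Appendix A 2.2 window, not identical to it: it takes all onsets whatever their cause and ends at dose 2.
6. Keep the whole-study tables, because HRIG exposure continues after Day 3.

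The cost is some SAP and protocol wording and a few more descriptive tables. Beyond the rule for missing onset times, no new data are needed.

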10.5.1. Primary PK Analysis

The primary efficacy analysis will be based on the primary PK population.

The primary hypothesis is that the proportion of subjects receiving BPL HRIG + active vaccine with an anti-rabies titer of ≥ 0.5 IU/mL will not be less than the corresponding proportion for subjects receiving comparator HRIG + active vaccine, by more than 0.1 at Visit 6. The Farrington and Manning test statistic will be used to assess the statistical comparison at a one-sided significance level of 0.025. It will be concluded that the BPL HRIG is non-inferior to the comparator HRIG if the lower limit of an exact binomial 95% confidence interval calculated from the Farrington-Manning score test is greater than the *a priori* set -10% non-inferiority margin.

An additional analysis will be performed to assess the impact of dosing/PK sampling not being performed on the designated day. See Section 10.7.2.

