10.7.1. Potential Interaction

Before treatment unblinding, timing of vaccine dosing at Visits 3-5 and PK sampling at visit 6, if not performed on the designated day, will be assessed as potential effect modifiers on the association between RVNA levels and treatment group in the primary PK analysis. A chi-square or fisher’s exact test, as appropriate, will be used to measure the association between the dichotomous indicator of receiving dose/PK sampling on the intended day [yes/no] and target level of RVNA titer reached [yes/no]. If the association is significant at the 0.05 level, a subgroup analysis including only subjects

who were dosed/sampled on the target day will be reported in addition to the full analysis.

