10.9. Determination of Sample Size

Statistical calculations indicate a minimum of 73 subjects per group is necessary. To allow for subject withdrawals or unevaluable data, approximately 81 subjects will be enrolled per group.

This study is powered based on a one-sided test with an overall study α of 0.05. A total of 162 subjects will be randomized to achieve 85% power with a one-sided significance level of 0.025.

This computation accounts for an expected 10% dropout rate resulting in 146 evaluable subjects. The following table outlines the underlying assumptions:

Table 7: The underlying assumptions

	Day 14 \geq 0.5 IU/mL
Non-inferiority margin	10%
Difference	0%
% success	98%

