7. GENERAL ANALYSIS CONVENTIONS

All tables, figures and listings will be produced using SAS (v9.4 or a more recent version).

Unless otherwise stated, categorical data will be presented using counts and percentages, whilst continuous variables will be presented using the mean, 95% confidence interval for the mean, standard deviation (SD), median, minimum, maximum, number of subjects (n) and number of missing subjects or data points. Minima and maxima will be quoted to the number of decimal places as recorded in the CRF; means, SDs and medians will be quoted to one further decimal place. Percentages will be rounded to one decimal place.

Subjects who withdraw from the analysis will have their data analyzed to the point of withdrawal. Subjects who complete all required assessments up to and including Day 14 will be eligible for the primary PK population. Other subjects who withdraw from the study will be eligible for the ITT population. Unblinded subjects will continue in study after being unblinded unless noted otherwise.

For the purpose of the statistical analyses visit labels may be used interchangeably as Visit and Day as in the table below regardless of actual timing of study visit. Sensitivity analyses will be performed to address any potential visit timing issues.

Visit Label	Visit 1	Visit 2	Visit 3	Visit 4	Visit 5	Visit 6	Visit 7	Visit 8	Visit 9
Intended Day	Day -28	Baseline, Day 0	Day 3	Day 5	Day 7	Day 14	Day 28	Day 49	Day 140

a. DEFINITION OF STATISTICAL SIGNIFICANCE

- Primary Efficacy Endpoint

The BPL HRIG treatment effect will be considered non-inferior to the active comparator HRIG treatment when the resultant p-value from the one-sided Farrington-Manning

Score Test for proportion difference is [REDACTED].

- Secondary Efficacy Endpoints

The secondary efficacy endpoint analyses will be considered statistically significant using a two-sided significance level of 0.05.

b. ANALYTIC POPULATIONS

The following analysis populations will be defined for this study.

- Intent-to-Treat [ITT] Population

The intent-to-treat (ITT) population will include all randomized subjects. All analyses will be performed using the ITT population.

- Safety Population

The safety population will be defined as all subjects who receive at least one dose of BPL HRIG / comparator HRIG. Safety data will be analyzed up to the point of withdrawal for applicable subjects. The safety population will be used for all safety analyses.

- Per Protocol [PP] Population

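### The timing check in SAP 8.i and protocol 10.7.1 tests a pooled timing-outcome association, not effect modification, and the on-schedule analysis is made conditional on it

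*SAP*

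**What the plan says.** The stated purpose is effect modification. SAP 8.i (Potential Interaction) reads "Before treatment unblinding, timing of vaccine dosing and PK sampling, if not performed on the designated day, will be assessed as potential effect modifiers" of the association between titer and treatment group, in the primary and secondary PK analyses. Protocol 10.7.1 says that timing "will be assessed as potential effect modifiers on the association between RVNA levels and treatment group", there for the primary PK analysis only, and limits the check to "timing of vaccine dosing at Visits 3-5 and PK sampling at visit 6".

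The specified test is a chi-square or Fisher test to "measure the association between the dichotomous indicator of receiving dose/PK sampling on the intended day" and whether the target titer was reached. Both variables are yes/no, and treatment is not in the table. The consequence follows: "If the association is significant at the 0.05 level, a subgroup analysis including only subjects" on the target day is reported beside the full analysis.

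Elsewhere the timing analysis carries no condition. Protocol 10.5.1 says "An additional analysis will be performed to assess the impact of dosing/PK sampling not being performed on the designated day". It points to Section 10.7.2, which covers non-compliers; timing is in 10.7.1. The opening of protocol 10.7, repeated at the opening of SAP 8.i, lists timing of vaccine dosing among the sensitivity analyses to be done. SAP 7, having allowed visit labels to be used whatever the actual date, adds "Sensitivity analyses will be performed to address any potential visit timing issues".

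**The concern.** Timing is an effect modifier if the difference between BPL HRIG and comparator depends on whether the subject was on schedule. A table that pools the arms does not address that. If off-day visits lower success equally in both arms, the test can be significant with no modification. If the arms move in opposite directions, the pooled association can vanish while modification is present.

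At stake is a supportive analysis. Since visits are analysed by label, the on-schedule analysis is the direct check that the primary result does not rest on mistimed doses or samples. The plan commits to it only if a test of a different question is significant, in a trial expected to have very few failures.

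**Working it through.** **Inputs.** Protocol 10.9: 98% success in both arms, margin 10 points, one-sided 0.025, 85% power, 73 per group, 162 randomized, 146 evaluable. SAP 8.i: threshold p<0.05. No document gives an expected number of off-day subjects, so every off-day count below is an assumption.

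**The plan's own figure.** Farrington-Manning sample size with restricted null proportions 0.8895 and 0.9895:

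- s0 = √(0.8895×0.1105 + 0.9895×0.0105) = 0.3296
- s1 = √(2×0.98×0.02) = 0.1980
- n = [(1.960×0.3296 + 1.036×0.1980)/0.10]² = 72.4, so 73 per group

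162 × 0.9 = 145.8, so 146 evaluable. The planning inputs reproduce.

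**How many failures the test has to work with.** Expected failures are 146 × 0.02 = 2.92. P(0) = 0.98^146 = 5%; P(0 or 1) = 21%. With so few failures Fisher is the applicable version (15 off-day subjects would have 15 × 0.02 = 0.3 expected failures).

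If all k failures fall among m off-day subjects, the smallest attainable Fisher p is C(m,k)/C(146,k):

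- k = 1: 7/146 = 0.048, but 8/146 = 0.055. With one failure and 8 or more off-day subjects, p<0.05 is impossible in that direction.
- k = 2: C(33,2)/C(146,2) = 528/10585 = 0.0499; C(34,2)/C(146,2) = 561/10585 = 0.053. With two failures it becomes impossible from 34 off-day subjects.

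**How often the condition is met.** P = ΣΣ Bin(a; m, f_off) × Bin(b; 146−m, f_on) × 1[two-sided Fisher p<0.05], with on-day failure f_on = 2%:

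| Off-day subjects (assumed) | Off-day success | P(p<0.05) |
|---|---|---|
| 15 | 98% | 1% |
| 15 | 90% | 25% |
| 15 | 88% | 33% |
| 15 | 80% | 65% |
| 22 | 85% | 62% |
| 30 | 88% | 54% |

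**Whether it responds to modification.** Same enumeration, with 15 off-day and 58 on-day subjects assumed per arm and on-day failure 2% in both arms:

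| Off-day failure, BPL v comparator | Modification? | P(p<0.05) |
|---|---|---|
| 30% v 30% | none | 99% |
| 4% v 0% | yes, no pooled association | 1.7% |
| 12% v 2% | 10 points, one arm | 22% |
| 22% v 2% | 20 points, one arm | 54% |

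The first row is near-certain significance with nothing modified. The second is modification that the pooled table cannot show.

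**What the unconditional analysis would offer.** Enumerated Farrington-Manning power at 98% v 98% is 88% with 73 per arm, 83% with 66 and 82% with 62. The last two correspond to roughly 10% and 15% off schedule.

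**The case against.** The best defence is that the screen is not blind to modification. In the one-arm scenarios above it is significant 22% and 54% of the time. A true treatment-by-timing Wald test on the risk-difference scale, in the same setting, has about 18% and 41% power. Complete cancellation is also bounded: at 98% success one arm can gain at most 2 points, so a cancelling modification is about 4 points, well inside the margin. A reader might infer that the test cannot detect modification. That is too strong; it is weak and non-specific.

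A reader might also infer that the condition will usually suppress the on-schedule analysis. The documents do not support that: they give no off-day count, and several of the tabulated cases exceed one half. The SAP also extends the check to secondary PK analyses, where earlier visits may have more failures; no rates are given. And the condition removes a commitment to report; it forbids nothing.

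Finally, protocol 10.7.2 (and, similarly, SAP 8.i) describes subjects without the first three vaccine doses at the specified time as not eligible for the primary PK population, and gives them worst-case and best-case analyses with no significance condition. On that reading the check mainly concerns Visit 6 sampling. But protocol 10.7.1 treats vaccine timing as varying within the primary analysis, so the passages disagree.

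These points limit the size of the problem. They do not supply the missing treatment term or explain why a pooled p-value should decide what is reported.

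**Conclusion.** Wrong as written. The documents name effect modification and specify a test of something else; that holds at any off-day count. The low information content follows from the plan's own 98%: in 21% of trials there would be at most one failure, and with 8 or more off-day subjects a single off-day failure cannot reach p<0.05. The 25%, 33% and 54% figures rest on assumed counts of 15 or 30 off-day subjects and assumed off-day success, so how often the check is silent remains conditional. The clash with the unconditional wording in protocol 10.5.1 and 10.7 and in SAP 7 needs no assumption.

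It is also tempting to say that off-schedule data favour non-inferiority. The documents do not establish a direction. An equal loss in both arms works against it: with off-day success of 88% in both arms and 30 off-day subjects, enumerated power falls from 88% to 73%. Dilution of a true 10-point deficit works the other way: if off-day subjects do not differ by arm, false non-inferiority rises from 1.9% to about 3% with 15 off-day and a little over 5% with 30.

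The effect is confined to a supportive analysis.

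**What to change.** - In SAP 8.i and protocol 10.7.1, delete the pooled test as a condition. Always report the primary Farrington-Manning analysis in on-schedule subjects, labelled supportive.
- After unblinding, show the treatment difference with a 95% CI separately for on-day and off-day subjects. Keep this descriptive, with no interaction-test condition, since that test would also have little power. Say in advance that the off-day interval will be wide: with 8 v 7 off-day subjects, all successes, the score lower limit is near −32 points.
- State what counts as on schedule. Protocol 7.4 and Appendix G give no window for Days 3 to 14.
- In the same edit, reconcile protocol 10.7.1 with protocol 10.7.2 and SAP 8.i on whether off-time vaccine dosing removes a subject from the primary PK population, and with SAP 7 on visit labels. Align the SAP and protocol on whether the check covers secondary analyses, and correct the cross-reference in protocol 10.5.1.

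The cost is wording, one or two extra tables, and a slightly smaller sample in the on-schedule analysis.
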